6.4 STUDY INTERVENTION/EXPERIMENTAL MANIPULATION ADHERENCE

Session facilitators will record participant attendance and submit attendance records to the project coordinator. Session facilitators will also record instances when a participant is removed or leaves, e.g. due to intoxication or disruptive behavior.

6.5 CONCOMITANT THERAPY

N/A

6.5.1 RESCUE THERAPY

N/A

7 STUDY INTERVENTION/EXPERIMENTAL MANIPULATION DISCONTINUATION AND PARTICIPANT DISCONTINUATION/WITHDRAWAL

7.1 DISCONTINUATION OF STUDY INTERVENTION/EXPERIMENTAL MANIPULATION

A subject may be discontinued from the MASLIHAT or TANSIHAT intervention group by the session facilitator or project coordinator if he is repeatedly disruptive or engages in hostile or aggressive behavior toward staff or other participants. When a subject discontinues from the group sessions but not from the study, remaining study procedures will be completed as indicated by the study protocol. The reason(s) for discontinuing the participant from the intervention will be recorded. The participant will be included in all future scheduled assessments, even though participation in the intervention was discontinued.

7.2 PARTICIPANT DISCONTINUATION/WITHDRAWAL FROM THE STUDY

Participants are free to withdraw from participation in the study at any time.

The investigator will discontinue a participant from the study for the following reasons:

- Failing to attend the first group session
- Lost-to-follow up; unable to contact subject (see **Section 7.3, Lost to Follow-Up**)
- Any event or medical condition or situation occurs such that continued collection of follow-up study data would not be in the best interest of the participant

The reason for participant discontinuation or withdrawal from the study will be recorded on the Withdrawal Case Report Form (CRF). Subjects who sign the informed consent form but do not receive the study intervention may be replaced. Subjects who sign the informed consent form and receive the MASLIHAT or Control (Healthy Lifestyle) intervention and subsequently withdraw, or are discontinued from the study, will not be replaced.

7.3 LOST TO FOLLOW-UP

A participant will be considered lost to follow-up if he fails to return for two consecutive scheduled visits and study staff are unable to contact the participant after at least 3 attempts. A participant who contacts research staff following an absence will be allowed to rejoin the study.

The following actions must be taken if a participant fails to return to the research center for a scheduled study visit:

- Project staff will attempt to contact the participant, reschedule the missed visit within 2 weeks, counsel the participant on the importance of maintaining the assigned visit schedule and ascertain if the participant wishes to and/or should continue in the study
- Before a participant is deemed lost to follow-up, project staff will make every effort to regain contact with the participant (where possible, 3 telephone calls and, if necessary, a visit to the participant's last known residential address). These contact attempts will be documented in the participant's study file.
- Should the participant continue to be unreachable, he or she will be considered to have withdrawn from the study with a primary reason of lost to follow-up.

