Retention. Participants will be enrolled only if they expect to remain in Moscow for the next 12 months, and they will be asked to notify the PRIZMA office if they are returning to Tajikistan prior to the study completion. Participant tracking and participant retention will build on successful strategies used by the investigators in achieving high follow-up rates with PWID or migrant populations in prior studies. One challenge of studying migrants is that they can disappear without warning due to legal difficulties or an unexpected reason to return to home. Many are without permanent residence. We will use a series of strategies to retain participants over time. Key contact information (work, residence, friends/family, regular “hang-outs”) will be collected at intake for follow-up interviewing and updated at each follow-up contact. Participants will be contacted by phone or other preferred arrangements prior to each MASLIHAT session or interview as a reminder. If a participant cannot be reached by phone or other contact methods after missing an appointment, the Moscow Project Coordinator will visit the person’s last known address or locations where he typically frequents, and inquire with his recruiter or network members.

Compensation: Participants will receive the customary compensation in Moscow of \$20.00 for each interview completed. Intervention participants will also receive transit passes to attend the group sessions at the PRIZMA Research Center.

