9.4.2 ANALYSIS OF THE PRIMARY ENDPOINT(S)

Relative frequency of syringe sharing, equipment sharing, and vaginal or anal sex without a condom in the past 3 months will be measured at each time point on a 7-point Likert-type scale (Never, Rarely, Less than half the time, About half the time, More than half the time, Most of the time, Always). We will analyze ordinal outcomes, and we will also dichotomize responses to analyze binary (none/any) outcomes.

We will conduct repeated measures mixed effects regressions with random intercepts for subject and recruitment site to test the effect of intervention condition on changes in the outcome variables. We will use ordinal logistic regression for ordinal outcomes and modified Poisson regression for binary outcomes. We will conduct a test of the proportional odds assumption with a likelihood ratio test comparing the proportional odds model with a non-proportional odds model.⁷⁴ We will include the interaction of time and participant type (intervention participant vs. network member) to test for differential effects. If the interaction term suggests differential effects ($p < .10$), we will stratify analyses by participant type. Sociodemographic characteristics (age, education, time in Moscow) will be included as covariates in the analysis if they are related to the outcome at baseline or if they vary significantly across conditions. All participants with at least one follow-up interview will be included in the analysis.

Dosage: If there is variability in attendance, we will estimate repeated measures mixed effect models predicting outcomes with session attendance and the interaction between time, intervention condition, and session attendance as predictors. A significant interaction effect will indicate that the effect of the intervention is moderated by session attendance.

Social Network Diffusion. Additional analyses among network members will examine associations between exposure to intervention concepts (i.e. conversations about health, drugs/alcohol HIV) and changes in outcomes over time.

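### Sections 7.2 and 7.3 discontinue an unreachable man as withdrawn, possibly months before the 12-month endpoint, and no passage requires a further attempt to reach him

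*Combined protocol and SAP*

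**What the plan says.** **Definition (7.3).** "A participant will be considered lost to follow-up if he fails to return for two consecutive scheduled visits" and, as a second condition, "study staff are unable to contact the participant after at least 3 attempts". Both must hold. The same paragraph lets a man who gets in touch after an absence come back into the study.

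**Action list (7.3).** It opens with "The following actions must be taken if a participant fails to return to the research center for a scheduled study visit", which is one visit. Staff are to try to reach him and "reschedule the missed visit within 2 weeks". They are also to telephone, and if need be go to his home, before he is classed as lost. The list ends: "Should the participant continue to be unreachable, he or she will be considered to have withdrawn from the study", with loss to follow-up recorded as the main reason.

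**Discontinuation (7.2).** The reasons for which the investigator will discontinue a man include "Lost-to-follow up; unable to contact subject". The other two are missing the first group session and a best-interest criterion.

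**Retention (5.5).** The protocol expects absences: "One challenge of studying migrants is that they can disappear without warning due to legal difficulties or an unexpected reason to return to home". It provides reminders before each session or interview. After a missed appointment with no contact, the coordinator goes to the man's address or usual places and asks his recruiter or network. No duration is given, and men already classed as lost are not mentioned.

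**Analysis.** Section 9.4.2: "All participants with at least one follow-up interview will be included in the analysis". Section 9.3 promises an intention-to-treat analysis of everyone with a baseline interview. The hypotheses in 9.1 concern 12 months after the intervention. The schedule in 1.3 places HIV tests at baseline and Visit 10 only, and HCV tests at baseline, Visit 8 and Visit 10.

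**The concern.** An unreachable man who has not withdrawn consent is handled as if he had left the trial. After that point the protocol asks nothing more of staff, even where the 9- and 12-month visits lie ahead. In a mobile population whose absences are foreseen, some men out of reach at months 3 and 6 may be in Moscow again at month 12.

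What is at stake is avoidable missing data at the time point of the hypotheses and at the only follow-up HIV test. Section 5.5 names legal difficulties and unplanned returns home as reasons for disappearing, so the loss may not be random. Section 9.4.1 itself plans to look for non-ignorable missingness.

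A smaller defect sits beside this. The definition in 7.3 needs two missed visits. The action list starts from one and does not say how many precede its final step.

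**Working it through.** **Timing.** Inputs are the visit days and windows in section 1.3: Visit 7, Day 125 ±14; Visit 8, Day 214 ±14; Visit 9, Day 304 ±21; Visit 10, Day 365 ±30. A visit is taken as missed when its window closes. The ranges run from the target day of the second missed visit to window close plus the two-week rescheduling period.

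- *Visits 7 and 8 missed.* The Visit 8 window closes at 214 + 14 = Day 228, and 365 − 228 = 137 days. Range: 365 − 214 = 151 down to 365 − (228 + 14) = 123 days. Visits 9 and 10 are both still ahead. To the end of the Visit 10 window: (365 + 30) − 228 = 167 days.
- *Visits 8 and 9 missed.* The Visit 9 window closes at 304 + 21 = Day 325, and 365 − 325 = 40 days. Range: 365 − 304 = 61 down to 365 − (325 + 14) = 26 days. Visit 10 is still ahead.
- *Visits 9 and 10 missed.* No scheduled visit remains, so the rule costs nothing.

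**What each man loses if he is not re-contacted and does not return.**

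- *Visits 7 and 8:* no follow-up interview, so he fails the 9.4.2 condition, although 9.3 would include him. He also has no 6-month HCV result and no 12-month HIV or HCV result.
- *Visits 8 and 9:* he has a Visit 7 interview and stays in the behavioural analysis. His 12-month interview and tests may be lost.

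**Room for loss in the design.** Section 9.2 allows up to 10% attrition of 140 index men and 15% of 280 network members: 14 + 42 = 56 of 420, or 13.3%. Retained men per site are 126/12 = 10.5, 238/12 = 19.8 and 364/12 = 30.3, which match the plan's 10, 20 and 30.

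For power, take an effective size per arm of 6m/(1 + (m − 1) × 0.05), with m men per site and alpha 0.01, assumed two-sided. At m = 10, 0.35 against 0.05 gives 81.6%, and 0.50 against 0.10 gives 93.9%. Both are consistent with the stated 80% and 90%.

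For index men with m = 140(1 − attrition)/12, 0.35 against 0.05 gives 83% power at 10% attrition, 79% at 20% and 75% at 30%. This is a simple design-effect approximation, not the three-level routine used for the plan, and the rate pairs were chosen within the plan's ranges. It shows that the margin for index men is thin. It does not show how much loss this rule causes.

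**The case against.** Several points on the other side are sound.

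- *The rule is not triggered by missed visits alone.* Three or more failed contacts are also needed, so a man who misses visits but can be reached does not qualify.
- *One missed visit.* A reader might infer that a single missed visit leads to withdrawal, which could then happen soon after Day 139 (125 + 14). The documents do not support giving that reading equal weight. The action list speaks of steps before a man is deemed lost and uses the term that the definition has just fixed. The wording needs aligning, no more.
- *Tracing stops.* A reader might also infer that tracing must end, or that self-contact is the sole way back. No sentence says either. Section 5.5 provides contact before each interview, and section 8.1 has missing test results flagged for follow-up by the coordinator. Neither, however, expressly covers a man already discontinued, so the gap remains.
- *Every lost man leaves the analysis.* This is true only of a man who misses Visits 7 and 8 and never returns.
- *A recoverable number.* A reader might treat the 56 men of the attrition allowance as the pool and apply a recovery fraction. That allowance is an upper limit on all loss, and no recovery rate is given. The pilot lost no peer educators and had complete follow-up for 95% of network members, over 6 months only, and the three missing had left Moscow. Men still abroad could not attend the 12-month interview, which section 8.1 places at the study office.
- *The contrast with 7.1.* Keeping men who stop the sessions in later assessments does not conflict with a status for men who cannot be found. The point does not rely on it.
- *Confidentiality.* Section 2.3.1 names its loss as the primary risk. Repeated inquiries about men who inject, some of them undocumented, add exposure. This stands and belongs in the cost.

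**Conclusion.** The point holds as a procedural weakness that is cheap to remove. Sections 7.2 and 7.3 together require discontinuation of a man who misses two consecutive visits and cannot be reached. The only written return is at his own initiative, and no passage requires another attempt at month 12. For Visits 7 and 8 this falls about 137 days (123 to 151) before Day 365, and for Visits 8 and 9 about 40 days (26 to 61).

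The loss of all follow-up data assumes that the man misses Visits 7 and 8, is not re-contacted and does not return. That the loss is non-random is plausible from the reasons in 5.5 but is not shown. How many men are affected or recoverable is unknown, and no figure should be attached to it.

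**What to change.** 1. In 7.2, remove loss to follow-up from the reasons for discontinuation. Leave the first-session and best-interest criteria as they are.
2. In 7.3, replace the definition and action list with one rule. A missed visit is recorded as missed. The man stays on the contact list unless he withdraws consent or meets the best-interest criterion. The section 5.5 contact steps are repeated at each remaining visit, including the 12-month interview and HIV/HCV testing.
3. Assign lost status only when the Visit 10 window closes (Day 395).

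The cost is a wording amendment, slightly more tracing work for the existing coordinator, and some added confidentiality exposure. The exposure can be limited by using only the contact methods that the man agreed to at intake.

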8 STUDY ASSESSMENTS AND PROCEDURES

8.1 ENDPOINT AND OTHER NON-SAFETY ASSESSMENTS

Eligibility pre-screening. Potential index and network participants will call the PRIZMA Research Center for preliminary screening. The project coordinator will explain the study requirements and schedule an appointment for the enrollment visit (index participant) or enrollment and baseline interview (network member).

Screening & Enrollment. Participant screening, enrollment, and informed consent will take place in a private room at the PRIZMA office. A trained interviewer will interview each potential subject for the intervention conditions or as network members to identify those who meet the criteria to participate. Injection drug use will be confirmed by the presence of injection marks (tracks), or if marks are not visible, asking the subject about the injection process using a series of questions designed to identify PWID. The interviewers will then explain the purpose and activities of the study to eligible subjects and obtain informed consent from those who indicate their willingness to participate. Contact information also will be collected from the enrollees for follow-up purposes and the participants will be given contact information for the study coordinator should they have further questions.

Index participants. Project staff will confirm the participant's willingness to recruit two other Tajik migrant MWID for interviewing. Participants will complete a brief social network survey to enumerate their IDU network, and they will be given two coupons to recruit network members who meet the study criteria for interviews. Coupons will be valid for 30 days. Index participants will return to complete the baseline interview after network participants have enrolled.

Network participants. Project staff will check the participant's recruitment coupon and confirm his relationship to the index person who recruited him before continuing to administer the baseline interview.

Interviews: Intervention participants and network members will complete computer-assisted personal interviews (CAPI) at baseline (prior to first intervention session), and at 3, 6, 9, and 12 months post-intervention. All baseline and 12-month interviews will be conducted in a private room at the PRIZMA office; intermediate follow-up interviews may be conducted at the PRIZMA office or at a location selected by the subject. Trained interviewers will administer the 60 to 90-minute questionnaire, using a computer-assisted personal interview (CAPI) system (Qualtrics) to record responses. For the more sensitive questions such as sexual behavior and STIs, the interviewer will instruct the participant to enter his responses. The CAPI system will ensure proper administration of skip sequences. For quality control purposes, 20% of interviews will be randomly selected to be audiotaped, and half of these audiotapes will be reviewed by [name] or [name] for quality assurance. Using electronic data capture and requiring timely data uploads will allow the data manager to monitor research progress and conduct quality control checks. The questionnaires were developed and tested with members of the population using cognitive interviewing (CI).⁶² Translations were validated using "back translation" with a member of the study population.

Self-report Measures

Background measures. The baseline interview includes measures of basic sociodemographic variables (education, marital status, migration history, religion), community involvement/social activities, and health (general health, STIs). The follow-up interviews also collect self-reported STIs since last interview.

Outcome measures. Primary outcome measures are syringe sharing in the past 3 months, and vaginal or anal sex without a condom in the past 3 months. Other measures include syringe cleaning methods, and the Alcohol Use Disorder Identification Test (AUDIT)⁶³ to assess alcohol consumption and alcohol-related problems at each time point.

Theoretical mediators. In addition to risk behavior, the questionnaire will assess theoretical mediators including HIV knowledge, risk awareness, behavioral norms, self-efficacy, depression, and loneliness. HIV knowledge is assessed with 16 true/false items; risk awareness is assessed with questions such as "How likely are you to get HIV?" and "How much do worry about HIV?" Behavioral norms⁶⁴⁻⁶⁶ will be assessed with questions such as "How many of your friends who shoot drugs use a needle after someone else, without bleaching or cleaning?" (descriptive norms), and "How many of your friends would disapprove if you shared a needle with a stranger?" (injunctive norms). Responses are given on a 5-point scale from 1 (none) to 5 (all). Self-efficacy for safer drug injection will be measured with six items adapted from the CIDUS-III study⁶⁷ (e.g., "I can avoid sharing a needle even if I am dope sick or in withdrawal"), rated on a four-point scale from "strongly agree" to "strongly disagree". Depression will be measured using the Centers for Epidemiological Studies Depression Scale -- Revised (CESD-R)⁶⁸, and loneliness will be measured using the UCLA Loneliness Scale⁶⁹.

Network penetration & diffusion. Diffusion of MASLIHAT messaging/norms at the network level will be assessed using measures successfully used by SHIELD and other public opinion leadership interventions such as asking network members as to how many (if any) MASLIHAT peer educators they know, whether anyone within their drug using network talked with them about HIV since they were last interviewed, and whether they talked about specific topics (e.g. condom use, syringe cleaning, HIV testing).

Peer educator personal development. Measures of peer educator personal development (in addition to knowledge and behavior change) will be administered at baseline and at 12-month follow-up, including self-esteem, self-efficacy, and substance use self-stigma. The 10 items of the Rosenberg Self-Esteem Scale^{70, 71} assess a person's overall evaluation of his or her worthiness as a human being, including subscales of self-competence and self-liking. Items are rated on a 4-point scale from 1 (strongly disagree) to 4 (strongly agree). The New General Self-Efficacy Scale⁷² includes 8 items to measure general self-efficacy (e.g. "I will be able to achieve most of the goals that I set for myself.") rated on a Likert scale from strongly disagree to strongly agree. Internalized stigma of substance use will be assessed with 6 items adapted from a measure of HIV stigma⁷³, rated on a 5-point Likert-type scale, e.g. "I feel ashamed of being a person who uses drugs".

Intervention engagement

Session facilitators will record participant attendance, note homework completion, and rate participant engagement at each session.

HIV/HCV counseling and testing.

Intervention participants and network members will be referred to the Moscow HIV Prevention Center (MHPC) for voluntary HIV/HCV rapid and confirmatory testing and counseling following the baseline interview, and later at the 6-month (HCV) and 12-month (HIV and HCV) follow-up. We chose to not require HIV testing as a condition of study enrollment as its impact on study recruitment and participation are unknown. Participants will be informed that their results will be shared with the research study unless they choose to opt out. We will explain the measures we will employ to maintain the confidentiality of the results.

We will give each participant a card with a code number on which test results will be reported. The testing code number will be separate from the research ID number used to identify interviews, and will

consist of a group number and an individual code. The list matching testing codes with research IDs will be kept in a secure REDCap database separate from locator data and interview data. Participants who object to having their test results linked to their personal interview data will be given the option of blacking out the individual code number, keeping only the group number. This will allow us to track results by intervention group even if the results cannot be linked to individuals.

OraSure OraQuick® ADVANCE HIV-1/2 (oral fluid) and OraQuick® HCV (finger stick) rapid antibody tests and confirmatory tests for positive results (HIV immunoassay and HCV RNA PCR) will be administered to participants by Moscow HIV Prevention Center (MHPC) staff. Test results will be collected from MHPC by PRIZMA staff. Missing test results will be flagged for follow-up by the project coordinator.

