Assess network penetration and diffusion among networks of MASLIHAT participants.	80% of MASLIHAT participant network members report conversations about syringe cleaning, condom use, etc.	The MASLIHAT intervention teaches participants to engage in peer education activities	

OBJECTIVES	ENDPOINTS	JUSTIFICATION FOR ENDPOINTS	PUTATIVE MECHANISMS OF ACTION

Assess changes in and mediating effects of HIV knowledge, risk awareness, behavioral norms, and self-efficacy among MASLIHAT participants and their network members compared to the TANSIHAT control condition.
 
Assess the mediating and moderating effects of depression and loneliness among MASLIHAT participants and their network members compared to the TANSIHAT control condition.
			
HIV knowledge, risk awareness, behavioral norms, and self-efficacy are theoretical mediators for intervention effects.
 
Depression and loneliness are indicators of psycho-social well-being that potentially mediates or moderates intervention effects.

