4.2 SCIENTIFIC RATIONALE FOR STUDY DESIGN

We will use a cluster-randomized design to prevent control group contamination due to the nature of the intervention. Because the intervention is designed to reach the participant's social network through peer education activities, individual randomization to condition is not feasible.

The Targeted Application of Network and Social Intervention on Health Assistance for Tajiks (TANSIHAT) program will serve as the control condition. TANSIHAT was adapted from the Healthy Lifestyles for Labor Migrants intervention designed by Drs. [name] and [name] to serve as a control condition in testing an HIV prevention model delivered to Tajik migrants. We expanded the program contents to include TB risk and prevention and organized it to be parallel to MASLIHAT in the number and length of sessions. This program provides relevant health information for Tajik migrant workers and encourages participants to share the information with other migrants, but it does not address HIV/STI risk and prevention, condom use, or drug use. It does address heavy alcohol use which will affect our ability to detect effects on drinking behavior.

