6.3 MEASURES TO MINIMIZE BIAS: RANDOMIZATION AND BLINDING

The 12 recruitment sites will be pair matched and randomly assigned to a study arm. One of each pair will be assigned to MASLIHAT and the other to the control condition. [name] will create the matched pairs based on site characteristics, and randomization will be determined by the PI using a random number generator. A random number will be generated for each site, and within each matched pair, the site with the smaller number will be assigned to MASLIHAT. To minimize bias during recruitment, site assignments will be masked from project staff engaged in recruitment. The PI will inform the Moscow project coordinator of the site assignment as needed for group scheduling, after the first cohort of participants has been filled for the site. Participants will be informed of their assignment at the time of scheduling the group sessions. [name] will also have access to this information as needed, after recruitment activities are underway. Interviewers will be blinded to site assignment, and the same interview instrument will be used for MASLIHAT and control condition participants. Session facilitators, who may become aware of the recruitment sites from which participants originated, will be instructed during training not to reveal this information to interviewers. Intentional or unintentional breaking of the blind is to be reported to the PI.

The randomization codes will be kept in a password-protected file accessible to the PI, co-investigators, the project coordinator, and the data manager. When preparing data for analysis, the data manager will

blind code recruitment site and study arm. Masking will be removed for reporting interim results to the DSMB.

In addition, we will adopt a position of clinical equipoise. Intervention facilitators and interviewers will be informed that we are testing two different interventions, but neither is assumed to be superior to the other. Facilitators will be assigned to one or the other, while interviewers will be blinded to participant condition. Data collection will be conducted by interviewers who are not involved in intervention delivery. Interviews will be standardized using a computer-assisted instrument, and sensitive sections will be self-administered.

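### The network-diffusion questions may suggest the trial arm to blinded interviewers, and the protocol does not say whether the sharing items are self-entered

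*Combined protocol and SAP*

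**What the plan says.** Section 6.3 (Randomization and Blinding): "Interviewers will be blinded to site assignment, and the same interview instrument will be used for MASLIHAT and control condition participants". It repeats that "interviewers will be blinded to participant condition" and adds, without naming them, that the sensitive parts of the interview are completed by the participant. It tells facilitators not to disclose recruitment sites to interviewers and asks that any break of the blind be reported to the PI.

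Section 8.1 (Interviews): trained interviewers deliver a 60 to 90-minute CAPI questionnaire at baseline and at 3, 6, 9 and 12 months. On self-entry: "For the more sensitive questions such as sexual behavior and STIs, the interviewer will instruct the participant to enter his responses". The same section lists syringe sharing in the past 3 months as a primary outcome measure.

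Section 8.1 (Network penetration & diffusion): network members are to be asked, among other things, "how many (if any) MASLIHAT peer educators they know" and "whether anyone within their drug using network talked with them about HIV since they were last interviewed", as well as whether specific topics such as condom use and syringe cleaning came up.

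Section 4.2, on the control programme: "it does not address HIV/STI risk and prevention, condom use, or drug use". Section 3 sets the exploratory diffusion target: "80% of MASLIHAT participant network members report conversations about syringe cleaning, condom use, etc".

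**The concern.** Blinding of interviewers is one of the few protections available here. The intervention cannot be hidden from index participants, and the primary outcomes are self-reported. Yet the questionnaire itself includes an item that names the experimental programme, and other items whose answers should differ between arms if the intervention diffuses as intended. An interviewer who hears those answers may form a view of the man's arm.

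If the sharing questions follow and are spoken aloud, tone, probing or coding could shift. The likely direction is fewer admitted sharing events among MASLIHAT network members, which would favour the intervention.

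The biological endpoints offer only a weak cross-check. Testing is voluntary, and Section 9.2 gives detectable rate ratios of only 0.11 for HIV and 0.21 for HCV.

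**Working it through.** **No stated figure is at issue.** The check is mainly a comparison of passages.

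*Does the instrument carry arm-related information?* Yes, through the answers. Being asked tells the interviewer nothing, because both arms get the same instrument. But the sites were cluster-randomised to limit contamination (Section 4.2), the control content omits the topics asked about (Section 4.2), and the target for MASLIHAT networks is 80% (Section 3). The better the diffusion, the more the answers separate the arms.

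*What has to be true for this to reach the outcome?* Three conditions:

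1. The interviewer learns the answer. Interviewer administration is the default in Section 8.1; the mode of the diffusion items is not stated.
2. Outcome items come afterwards, either later in the same interview or at a later visit with the same interviewer. Neither the item order nor the assignment of interviewers to visits is stated. If the items are first asked at month 3, three further interviews follow (months 6, 9 and 12).
3. The outcome item is asked aloud. Sexual behaviour is named as self-entered, so condomless sex is protected. Syringe and equipment sharing is not named, but the list is only of examples and Section 6.3 speaks generally of sensitive parts.

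The documents neither establish nor exclude the chain.

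*Do the other safeguards close it?* The instruction to facilitators concerns facilitators. Reporting to the PI comes after the event. Interviewers are told that neither programme is presumed better, and 20% of interviews are audiotaped, with half of those recordings reviewed. These reduce the risk but do not stop the questionnaire from disclosing the arm. No assessment of whether blinding succeeded is described.

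*Who is affected?* The items go to network members: 280 enrolled, 280 / 2 = 140 per arm. Bias of the kind described would arise mainly among the 140 in the MASLIHAT arm.

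**Illustration of sensitivity (assumed bias, not an estimate).** The documents give no size for under-reporting caused by an interviewer's knowledge of arm, so I assume x percentage points across MASLIHAT network members, with no true effect.

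- Inputs from Section 9.2: 20 network members per site and ICC 0.05. There are 6 sites per arm (12 sites, pair matched).
- Design effect = 1 + (20 − 1) × 0.05 = 1.95.
- Effective n per arm = 6 × 20 / 1.95 = 61.5.
- Chance of a false result favouring MASLIHAT = Φ[(x − z√(2p̄(1 − p̄)/n)) / √((p₁(1 − p₁) + p₂(1 − p₂))/n)], where p₁ is the true rate, p₂ = p₁ − x, and p̄ is their mean.
- Example, true sharing 40%, x = 10 points, two-sided 0.05: (0.10 − 1.96 × √(0.455/61.5)) / √(0.45/61.5) = (0.10 − 1.96 × 0.0860) / 0.0855 = −0.80, giving 21%.

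| Assumed x | Share of true sharers concealing (x / 40) | Two-sided 0.05 | Two-sided 0.01 |
|---|---|---|---|
| 0 | 0 | 2.5% | 0.5% |
| 5 points | 12.5% | 8% | 2% |
| 10 points | 25% | 21% | 8% |
| 15 points | 37.5% | 43% | 21% |

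For true rates from 30% to 50%, the 10-point case gives 20% to 25% at 0.05. This is a two-level approximation to the three-level procedure used in the plan.

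**The case against.** A reader might go further and infer that the arm is revealed at month 3, stays known for every later visit, and that syringe sharing is asked aloud. The documents support none of these as fact.

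- Section 8.1 gives examples of diffusion questions, not the questionnaire. A MASLIHAT network member may not know the programme's name and may answer none; a control man may know a MASLIHAT educator.
- The wording about the period since the last interview belongs to the HIV-conversation item. Nothing says at which visits the item naming MASLIHAT is asked, or that the same interviewer returns.
- The self-entry list is illustrative and Section 6.3 is broader. Injection questions may already be self-entered.
- Social desirability does not need an unblinded interviewer. Index participants are told their assignment, and network members know what their peers have told them. Changing the questionnaire leaves that untouched.

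All of this stands, and it limits the point to a risk left open. It does not answer the mismatch: an interviewer-administered questionnaire that collects arm-related answers sits beside a promise of interviewer blinding, and no stated rule on order or mode keeps the two apart.

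**Conclusion.** The point holds as a low-cost improvement, not as a demonstrated failure of blinding. Followed as written, Sections 8.1 and 6.3 allow the interviewer to hear answers that may strongly suggest the arm before recording a self-reported primary outcome.

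The conclusion rests on the diffusion items being asked aloud under the default mode, and on at least some sharing items following them without self-entry; neither is stated. Effects on later visits need the further assumption that the same interviewer returns. The claim that sharing is unprotected cannot be made: the text is unclear, and that part is mainly a request for clarification.

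The size is unknown and would concern mainly about 140 network members. The illustration shows only that, if such bias existed, 5 to 10 points would raise the false-positive chance in MASLIHAT's favour from 2.5% to between 8% and 21% at two-sided 0.05, under the stated assumptions.

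**What to change.** - In Section 8.1 (Network penetration & diffusion), place the diffusion questions at the end of the CAPI and have the participant enter the answers himself, out of the interviewer's view. Self-entry also guards against carry-over to later visits, which placement alone does not.
- In Section 8.1 (Interviews), state that syringe and equipment sharing items are self-entered at every visit. If that is already the practice, one sentence settles it.

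The cost is a small change of order and mode in the existing Qualtrics instrument and slightly more self-entry for participants. Sample size, visits and analysis are unaffected. The change does not remove reporting bias in men who know their own assignment, and the report should say so.
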